Appendix 7 – E-consent	

## **PROTOCOL SUMMARY AND/OR SCHEMA**

We propose a clinical trial examining the use of perioperative pregabalin to decrease opioid usage after ureteroscopy with stent placement. Patients undergoing ureteroscopy with stent placement will receive either a single dose of 300 mg pregabalin PO or an identical placebo in the preoperative area. We will assess patient centered outcomes, specifically examining possible side effects as well as short- and long-term opioid sparing effects.

## **OBJECTIVES AND SCIENTIFIC AIMS**

#### Primary Hypothesis

The use of perioperative pregabalin in ureteroscopy with stent placement will decrease the amount of perioperative pain experienced by the patient.

#### Secondary Hypotheses

We hypothesize that the use of the perioperative pregabalin in ureteroscopy with stent placement will:

- Have secondary benefits in the immediate post-operative period
- Decrease the proportion of patients receiving opioid prescription in the first 30 post-operative days
- Not decrease patient satisfaction with their procedure
- Not significantly increase the risk of adverse outcomes
- Decrease the risk of new persistent opioid use at 3, 6, and 12 months after surgery

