## BACKGROUND AND STUDY DESIGN/INTERVENTION

The prevalence of urolithiasis is greater than 8% and increasing in the United States (US) [1]. There are several treatment options, including ureteroscopy (with or without laser lithotripsy), extracorporeal shock wave lithotripsy, and percutaneous nephrolithotomy. A recent study in California demonstrated that ureteroscopic treatment was employed in more than 40% of interventions [2], with some nationwide estimates up to 59% [3]. At least 300,000 stone interventions are performed yearly in the US on working age adults [4], thereby, there are at least 120,000 ureteroscopies. There are several other indications for ureteroscopy, including diagnosis of structural anomaly and diagnosis and management of ureteral and renal pelvic tumors.

Depending on the specifics of the procedure, it may be advisable to place a ureteral stent intraoperatively [5]. The most commonly used variety of stent is the double J stent [6], which has long been known to cause post-operative pain in around 80% of patients, as well as irritative symptoms in a sizeable portion [7, 8]. Approximately 12% of those undergoing ureteroscopy will have an emergency department (ED) visit in the first 30 post-operative days [9], typically for stent related symptoms or post procedural pain [10]. Aside from the short-term repercussions of ureteroscopy with stent placement (such as ED visits), there are long-term issues related to pain or the treatment thereof. Recent evidence suggests that approximately 6% of opioid naïve patients who undergo ureteroscopy will become new persistent opioid users [11].

Alpha-blockers decrease ureteral stent discomfort when compared to placebo [12, 13]. Anti-muscarinic medications have also been shown to be helpful with stent related discomfort independently, or in addition to alpha blockade [14], though the evidence is mixed [15]. A recent systematic review failed to find any studies of other medications for stent related discomfort that met inclusion criteria [16]. Subsequently, a well-designed study demonstrated the utility of mirabegron for indwelling stent symptoms [17].

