#### Analysis

A formal statistical analysis plan, crafted by the study team in partnership with the statistical consultants, will be finalized prior to data analysis.

The primary outcome will be the score on the visual analog scale of pain in the PACU. Secondary outcomes reported will be the amount of opioid prescribed (in oral morphine equivalents) in the first thirty post operative days. Also reported will be the proportion of patients requiring narcotic pain medication, a composite of unplanned healthcare interactions within the first 30 post-operative days, PACU length of stay, nausea/vomiting, changes in cognition or coordination, and a composite of serious adverse events (ICU admission or death) within the 30 post-operative days.

Analyses will be performed in R. For the primary outcome, student's t-test will be used to compare the amount of opioid prescribed. For the secondary outcomes, either chi-squared or student's t-test will be performed to test for differences between those who received perioperative pregabalin and those who received placebo. For the secondary outcomes, multiple testing will be corrected using the Benjamini-Hochberg method [31].

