Perioperative pregabalin as part of a multimodal treatment plan for pain after ureteroscopy with stent placement: a randomized, controlled trial

Statistical analysis plan

Version 1.0 Version date: February 27, 2020

Statistical Analysis Plan

Enrolled subjects' characteristics will be summarized using mean \pm SD for continuous variables and proportions for categorical variables. The primary outcome of interest, the value on the visual analog scale of pain score (VAS score), will be summarized overall and by treatment group, those who received perioperative pregabalin and those who received placebo. To examine the research question, an independent sample t-test will be conducted to assess if differences exist on VAS scores by the treatment group. The assumptions of normality and homogeneity of variance will be assessed. Normality of the scores will be assessed using the One-Sample Kolmogorov-Smirnov test. Homogeneity of variance will be assessed using Levene's Test for the Equality of Error Variances. The *t*-test will be two- tailed with the probability of rejecting the null hypothesis when it is true set at *p* < 0.05. If groups are unbalanced with respect to one or more patients' characteristics, we will perform a stratified analysis of VAS scores based on that characteristics.

For the secondary outcomes of interest, a two sample t-test or a Chi-square test of independency will be used to compare the treatment groups for continuous and categorical outcomes, respectively. In addition to univariate analysis, we will fit a generalized linear model or logistic regression model of outcome on treatment group controlling for possible confounding variables such as, gender, age, pre-operation VAS score and pre-operation Watson clock drawing score, depending on type of outcome.

Power Analysis

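### The two no-worse secondary hypotheses (satisfaction, adverse outcomes) have only difference tests and outcome models behind them, with no margin or confidence-interval criterion

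*Protocol*

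**What the plan says.** Two of the Protocol's Secondary Hypotheses claim that the drug is no worse than placebo: it will "Not decrease patient satisfaction with their procedure" and "Not significantly increase the risk of adverse outcomes". The second carries a significance word; the first carries no criterion.

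For secondary outcomes the Protocol's Analysis section says that "either chi-squared or student's t-test will be performed to test for differences" between the arms. The SAP says that "a two sample t-test or a Chi-square test of independency will be used to compare the treatment groups" and adds that "we will fit a generalized linear model or logistic regression model of outcome on treatment group", with adjustment for possible confounders. The SAP's Power Analysis covers only the VAS score.

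Two further places bear on the same aims.

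- **Multiplicity.** The Protocol's Analysis section states: "For the secondary outcomes, multiple testing will be corrected using the Benjamini-Hochberg method". The outcomes it lists include nausea/vomiting, cognition or coordination changes, and "a composite of serious adverse events (ICU admission or death) within the 30 post-operative days". Satisfaction, a listed Secondary Endpoint, is not named there. The SAP does not mention the correction.
- **PACU form.** The section on outcome assessment calls the PACU questionnaire optional and assigns it to nurses. The evaluation schedule lists a PACU form with study staff as respondent, under a lead-in saying that the protocol requires these evaluations. Both sections on toxicities and side effects say, without qualification, that side effects will be recorded in the PACU questionnaire or in questionnaires.

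**The concern.** A non-significant difference test shows that the data did not rule out equality. It does not show that a harm is absent or small. When the hypothesis itself is worded as the absence of a significant increase, fewer patients and more missing data both make it easier to meet. The Protocol Summary gives side effects as a specific purpose of the trial, and the Background names cognition and coordination changes as the drug's principal side effects. A report that these were not significantly increased could be read as evidence of safety that the design cannot supply. The same holds for satisfaction, where both documents expect heavy loss to follow-up.

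A Benjamini-Hochberg adjustment, if it covers harms, can only make a harm signal harder to declare. A PACU form that may be skipped would leave the PACU-symptom endpoint exposed to selective missing data.

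**Working it through.** **1. The plan's own figure.** SAP Power Analysis inputs: difference 1 VAS unit, SDs 1 and 2.5, two-sided alpha 0.05, power 80%.

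- Normal approximation: n = (1² + 2.5²)(1.960 + 0.842)² / 1² = 56.9, so 57 per group.
- Unequal-variance t-test (noncentral t): power 79.7% at 58 and 80.4% at 59. The stated 59 reproduces.
- Dropout of 40%: 118 / 0.60 = 197, so about 200 reproduces.

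This sizes the trial for VAS. No corresponding figure exists for satisfaction or any harm.

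**2. Patients available.** All 200 evaluable gives 100 per group, the best case for same-day and chart-review outcomes. For questionnaires, 100 × 0.60 = 60 per group (SAP dropout) or 100 × 0.50 = 50 (Protocol Sample Size loss).

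**3. How often a true rise in a harm is non-significant.** The documents give no drug-harm rate, so all rates here are assumptions. Method: exact enumeration over two binomials, uncorrected Pearson chi-squared, two-sided 0.05, 100 per group.

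| True rates, placebo vs pregabalin | Non-significant | With continuity correction |
|---|---|---|
| 5% vs 15% | 32% | 43% |
| 10% vs 20% | 48% | 57% |
| 20% vs 30% | 63% | 69% |
| 30% vs 40% | 68% | 74% |
| 10% vs 30% | 4% | 7% |
| 20% vs 40% | 12% | 16% |
| 30% vs 50% | 17% | 21% |

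**4. Unplanned contacts within 30 days.** The only related rate in the Background is the 12% of patients with an ED visit, and those visits are described as "typically for stent related symptoms or post procedural pain", so it is not a drug-harm rate. The Secondary Endpoints define a number of contacts, so the following applies only if the endpoint is analysed as a proportion. At 100 per group a true 18% against 12% is non-significant 78% of the time, and 24% against 12% is non-significant 39% of the time. With 12% in both arms the 95% CI half-width is 1.96 × √(2 × 0.12 × 0.88 / 100) = 0.090, or 9 points.

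**5. Continuous outcomes.** Two-sample t-test, assumed worsening of 0.3 SD, noncentrality 0.3 × √(n/2).

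| Per group | Noncentrality | Non-significant |
|---|---|---|
| 100 | 2.12 | 44% |
| 60 | 1.64 | 63% |
| 50 | 1.50 | 68% |

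The first row fits the clock score with complete data. All three apply to satisfaction, depending on loss.

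**6. ICU admission or death.** If none of 100 patients in an arm has an event, the exact upper limit is 1 − 0.025^(1/100) = 0.036, or 3.6%.

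**7. The PACU form, side by side.** Status differs (optional against listed as required) and so does the respondent (nurses against study staff). The appendix only refers to a separate instruments file, so whether this is one form or two cannot be settled from the documents.

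**The case against.** These are broad secondary hypotheses, for which difference tests are customary, and no passage says that safety will be concluded from a p-value above 0.05. The word significantly might mean materially. This stands in part: the defect is an unstated criterion, not a stated wrong inference. It does not remove the problem, because the analysis offers nothing except a significance test or a model against which the hypothesis could be judged.

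A reader might infer that moderate harms would be missed more often than not. The figures do not support that as a general statement. At 100 per group with the uncorrected test, 5% to 15%, 10% to 20%, 12% to 24% and a 0.3 SD worsening are each missed less than half the time, and 20-point rises from 10% to 30% are usually detected. The result depends on the assumed base rate.

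A reader might also infer that the two documents contradict each other on Benjamini-Hochberg. They do not: the SAP is silent, which is a gap. It is also not certain that harms are in the corrected family, because the Protocol names the opioid amount as the secondary outcome and then introduces the others as also reported.

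On the PACU form, the differing respondents would fit two forms as well as one inconsistent description. The schedule's lead-in also covers event-driven and untimed items, so it does not clearly make every row mandatory. Blinding with identical-looking medication limits differential completion between arms, although completion could still depend on symptoms.

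**Conclusion.** The concern holds for the two hypotheses. Neither document gives a criterion by which no decrease in satisfaction or no increase in adverse outcomes could be concluded, and the natural reading of the adverse-outcome wording rewards low power. Under the assumed rates, with all 200 patients evaluable, a 10-point rise in a harm is missed 32% to 68% of the time. A 0.3 SD fall in satisfaction is missed 44% of the time with complete data and 63% to 68% at the planned losses. Moderate harms would often, though not always, be missed; large ones usually would not.

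That conclusion does not rest on any one assumed rate, since non-significance is not evidence of no harm at any of them. The multiplicity and PACU-form points are secondary: the first is an omission in the SAP together with an undefined family, and the second is a textual inconsistency if there is one form and a missing explanation if there are two. Outcomes with other sources (clock test, chart review, unanticipated contact, patient questionnaires) are not affected by the PACU-form point.

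**What to change.** 1. Restate both hypotheses as estimation aims and drop the word significantly. Report between-group differences in satisfaction, unplanned contacts, PACU symptoms, clock score and ICU admission or death with 95% CIs, exact for rare events. The SAP's models can supply adjusted estimates. State in both documents that no increase or no decrease will not be concluded from a non-significant test.
2. Define the same Benjamini-Hochberg family in the Protocol and the SAP, say whether harms and satisfaction belong to it, and state that an adjusted non-significant p-value will not be used as evidence of no harm.
3. If there is one PACU form, reconcile the sections so that the form behind the PACU-symptom endpoint is completed for every randomised patient, and report completion by arm. If there are two forms, say so and name the one that feeds the endpoint.

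The first two changes cost only wording and no patients, but some no-harm statements will become inconclusive. The third may add staff time, by an amount that cannot be judged because the form is not shown. The Background reports that the pilot's surveys burdened participants, nurses and study staff, so making the form optional may have been deliberate.

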#### Primary Endpoints

The primary endpoint will be the value on the visual analog scale of pain score supplied by the patient approximately one hour after reaching the post-operative area.

#### Secondary Endpoints:

Secondary endpoints include the following:

- Reported post anesthesia care unit (PACU) symptoms experienced
- Score on clock drawing test
- Number of unplanned contacts between the patient and the healthcare system within 30 days
- Reported satisfaction at 7- and 30-days post procedure
- Proportion of patients with new persistent opioid use at 3, 6, and 12 months after surgery

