### **EVALUATION DURING TREATMENT/INTERVENTION**

#### Not part of usual care

This protocol requires several evaluations outside those typically used. These are all questionnaires.

Timing	Questionnaire	Respondent
Before day of surgery OR on day of surgery	Screening questionnaire	Study staff
	Baseline questionnaire and demographic information	Patient
	E-consent	Patient
	Preop Watson clock drawing test and visual analog scale of pain	Patient
Day of surgery	PACU	Study staff
	Watson clock drawing test and visual analog scale of pain \$	Patient
3 days post op	Early patient questionnaire	Patient
7 days post op	Early patient questionnaire	Patient
30 days post op	30 days post op chart review	Study staff
	Early patient questionnaire \$	Patient
90 days post op	Late patient questionnaire	Patient
6 months post op	Late patient questionnaire	Patient
1-year post op	Late patient questionnaire	Patient
	1-year post op chart review	Study staff
Untimed	Unanticipated contact	Study staff/Treatment staff
	Evaluation of trial	Patient

\$ indicates questionnaires for which compensation will be provided. Please see details of compensation.

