### **CRITERIA FOR THERAPEUTIC RESPONSE/OUTCOME ASSESSMENT**

The intraoperative period is defined as the period from anesthesia induction to the extubation of the trachea. The surgical time is determined from the incision to the final skin closure.

The postoperative period is defined as the period from the extubation to various study endpoints.

Blood loss is defined as the estimate accounted from the suction device and absorptive sponges during the procedure, as described and agreed upon by the surgeon, anesthesiologist, circulating nurse, and surgical technician as covered by institutional guidelines.

The patient's pain will be evaluated with a visual analogue scale of pain [28]. This may either be done digitally or by paper [29].

Adverse events will be measured with an optional PACU questionnaire for nurses as well as by monitoring of unanticipated contact.

Neurological changes will be measured using the Watson[30] clock drawing test.

Satisfaction will be evaluated via questionnaires at subsequent time points.

Need for opioid pain medication will be carefully tracked via patient questionnaire, chart review, and review of any available prescription database.

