Group sample sizes of 59 per group achieve 80% power to reject the null hypothesis of equal means when the population mean difference in VAS score is as little as 1 unit, assuming the standard deviations of 1 for group 1 (based on our pilot study) and 2.5 for group 2 (from literature), and with a significance level (alpha) of 0.05 using a two-sided two-sample unequal-variance t-test. Assumption about 40% dropout rate, it requires approximately 200 total subjects with a planned 1:1 placebo to active treatment enrollment ratio. We estimate at least 500 eligible procedures are conducted each year at our institution. Accounting for excluded patients and those who do not wish to participate, we estimate that full enrollment should be attainable within one year.

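### Satisfaction is collected repeatedly, but the planned methods compare the arms one visit at a time among that visit's responders; a joint model is a cheap, modest improvement

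*Protocol*

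**What the plan says.** The protocol's Secondary Hypotheses contain one statement on satisfaction, that pregabalin will "Not decrease patient satisfaction with their procedure". It names no day. Under Secondary Endpoints this becomes "Reported satisfaction at 7- and 30-days post procedure", with neither day marked as the main one. The questionnaire table (Not part of usual care) lists an "Early patient questionnaire" at days 3, 7 and 30. That table and the Patient incentives section offer payment for the day-30 form but not for the day-3 or day-7 form. On content, the outcome-assessment section says only that "Satisfaction will be evaluated via questionnaires at subsequent time points"; the form itself is in an appendix file that is not part of the documents.

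For secondary outcomes the SAP states that "a two sample t-test or a Chi-square test of independency will be used to compare the treatment groups for continuous and categorical outcomes". It adds a generalized linear or logistic model of the outcome on treatment and baseline covariates. The protocol's Analysis section likewise names a t-test or chi-square test. Neither document gives a time term, a within-patient correlation or a missing-data method for satisfaction.

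On loss, the SAP's Power Analysis has "Assumption about 40% dropout rate", while the protocol's Sample Size section assumes 50%.

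**The concern.** None of the listed methods takes two measurements from one patient. Although no sentence says so, days 7 and 30 would therefore each be compared among the patients who returned that day's form. Two things follow.

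- **Selection.** With 40 to 50% of forms possibly missing, a comparison of responders estimates the effect in all randomised patients only if returning the form is unrelated to satisfaction within each arm. (Selection of the same kind and strength in both arms may cancel, but that cannot be relied on.) Payment at one visit only makes it plausible that the two responder sets differ.
- **Information.** A patient's day-7 answer says something about a missing day-30 answer, and the reverse. Separate comparisons discard it.

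At stake are the accuracy and width of the satisfaction estimates. The primary pain analysis is not affected.

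**Working it through.** **1. The plan's own figures.** No power is stated for satisfaction. The sample size for the primary pain score (SDs 1 and 2.5, difference 1, two-sided 0.05, unequal-variance t-test) reproduces: 59 per group gives 80.4% power. With 118 patients, 118/(1 − 0.40) = 197, close to the stated 200. The protocol's 50% would give 118/(1 − 0.50) = 236. The 40% and 50% are loss rates for the trial as a whole; here they stand in for survey non-response, which the documents do not give.

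**2. Precision of each day's difference.** Assumptions: 100 randomised per arm, 60 answering each form, SD 1 on both days, within-patient correlation ρ of 0.5 to 0.7. Let b patients per arm answer both forms and o = 60 − b answer one only, for each day.

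- Separate comparison: SE = √(2/60) = 0.1826.
- Joint model: the per-arm information matrix has diagonal A = b/(1 − ρ²) + o and off-diagonal C = −bρ/(1 − ρ²). The variance of one day's mean is A/(A² − C²), and SE = √(2 × variance).
- Example, responses independent across days (b = 36, o = 24), ρ = 0.7: A = 70.59 + 24 = 94.59, C = −49.41, variance = 0.01454, SE = 0.1705. Reduction: 1 − 0.1705/0.1826 = 6.6%.

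| Both forms, per arm | ρ = 0.5 | ρ = 0.7 |
|---|---|---|
| 36 (independent) | 3.2% | 6.6% |
| 45 | 2.4% | 4.9% |
| 60 (same patients) | 0% | 0% |

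With the protocol's 50% loss the range is again about 0 to 7%: 7.2% for b = 25 and ρ = 0.7, and 0% if the same 50 answer both. In the best 60% case the 95% CI half-width falls from 1.96 × 0.1826 = 0.36 SD to 1.96 × 0.1705 = 0.33 SD.

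**3. Bias.** Suppose there is no treatment effect, day-30 forms in one arm come from a random 60%, and in the other arm from patients whose mean day-7 score lies Δ above that of their arm. With normal scores the day-30 responder comparison is then wrong by ρ × Δ. For ρ = 0.6 and Δ = 0.30 that is 0.18 SD.

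A simulation agrees (ρ = 0.6; in one arm the chance of a day-30 form rises with the day-7 answer, probit slope 0.5, 60% overall):

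- All patients answer day 7: Δ = 0.29, separate comparison off by 0.17 SD, joint estimate off by 0.00.
- Only 60% answer day 7, and day-30 response is random among the rest: Δ = 0.17, separate comparison off by 0.10 SD, joint estimate 0.00.

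These sizes illustrate a mechanism; nothing in the documents says how strong it is.

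**4. Averaging the two days.** Under the assumptions of step 2 the average has SE = 1/√(A + C): 0.1443 for b = 36, ρ = 0.5, and 0.1683 for b = 60, ρ = 0.7. Power is about Φ(effect/SE − 1.96).

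- Effect 0.45 SD on both days: one separate test, 0.45/0.1826 = 2.46, about 69%. Average: 0.45/0.1683 = 2.67 to 0.45/0.1443 = 3.12, that is 76 to 88%.
- Effect 0.45 SD on day 7 and none on day 30: the average effect is 0.225, and power is 27 to 34%, against about 69% for the day-7 test.

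**The case against.** The strongest reply is that two day-specific comparisons are a legitimate analysis. The endpoint names both days, the treatment is a single preoperative dose, and the pilot account in the Background shows that stent removal can fall inside the 30-day window, so the days may differ clinically. This stands, and it is why the recommended model keeps a separate difference for each day.

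Three stronger readings are tempting and should not be drawn.

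- **That separate testing costs much power against a pooled result.** This holds only if the effect is similar on both days, which nothing in the documents establishes; step 4 shows the reverse case. Setting one separate test against the average also flatters the average: two tests corrected as a pair have about 73 to 80% power to find an effect on at least one day, against 76 to 88% for the average.
- **That satisfaction takes two places in the Benjamini-Hochberg family.** The protocol's Analysis section applies that correction to secondary outcomes, but its own list omits satisfaction, and the SAP has no multiplicity rule. One place fewer would in any case matter little: for a 0.5 SD difference with 60 per arm, first-rank power moves from 47.3% with 10 entries to 48.6% with 9.
- **That partial responders are ignored.** A patient with one form counts fully in that day's test. What is lost is the information between visits.

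It is also fair to say that the item and its scale are not available. Shared content across visits is inferred from the form's name, and the SD-based figures may not suit an ordinal or binary item.

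**Conclusion.** The point holds as a modest improvement to a secondary analysis. The documents provide only cross-sectional methods for an outcome collected repeatedly with heavy expected loss, and give no method for the missing forms. A joint model lowers each day's standard error by about 0 to 7% (60% response, ρ 0.5 to 0.7, both assumed), with no gain in precision if the same patients answer both forms. Its more useful property is protection against bias when response depends on satisfaction already observed. It does not protect when response depends on satisfaction that was never recorded.

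The conclusion assumes that the same item appears on each form and that separate comparison is intended, which the listed methods imply but do not state. A separate gap remains under either analysis: the hypothesis is one of no decrease, yet no margin is given, so a non-significant difference would not support it.

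**What to change.** In the SAP, specify one repeated-measures model for satisfaction with treatment, day and treatment-by-day terms and an unstructured within-patient covariance, or an ordinal or binary equivalent if the item is not continuous. Use every randomised patient with at least one answer, and include day 3 if the item is on that form. Report the day-7 and day-30 treatment differences from this model with 95% CIs, and the number answering each form by arm. If the team wants a single result, the average of the two days may be prespecified, with the day-specific differences kept beside it.

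The cost is SAP wording and a standard model in R, which the protocol already names; no new data or visits are needed. The downsides are slightly more complex modelling and reliance on a missing-at-random assumption, which should be stated.
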